- Absence of progressive tumor at critical anatomical sites (e.g., cord compression) requiring urgent alternative medical intervention.

In determining whether or not the tumor burden has increased or decreased per irRECIST, the local site Investigator should consider all target and non-target lesions as well as any incremental new lesion(s). Scenarios where PD is confirmed at repeat imaging if any of the following occur by irRECIST:

- Tumor burden remains $\geq 20\%$ and at least 5 mm absolute increase compared to nadir.
- Non-target disease resulting in initial PD is worse (qualitative assessment).
- New lesion resulting in initial PD is worse (qualitative assessment).
- Additional new lesion(s) since last evaluation.
- Additional new non-target progression since last evaluation.

If repeat imaging confirms PD due to any of the scenarios listed above, subjects will be discontinued from study therapy. If repeat imaging does not confirm PD by irRECIST and the

subject continues to be clinically stable, treatment may continue and follow the regular imaging schedule.

*Note: If a subject with confirmed radiographic PD per irRECIST, but the subject is achieving a clinically meaningful benefit, and there is no further increase in the tumor burden at the confirmatory tumor imaging, an exception to continue treatment may be considered following consultation with the Sponsor. In this case, if treatment is continued, tumor imaging should continue to be performed following the intervals as outlined in **Appendix 1**.*

*Note: In subjects who discontinue study treatment without documented PD, every effort should be made to continue monitoring their disease status by tumor imaging following the intervals as outlined in **Appendix 1** until the start of new anti-cancer treatment, PD, death, or the EoS, whichever occurs first.*

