1.4 Study Design

A total of 18 patients with unresectable locally advanced or metastatic PSqCC will be enrolled into this trial.

INCMGA00012 should be administered intravenously, at flat dose of 500 mg over one hour (\pm 15 minutes) or 30 minutes (-5/+ 15 min) using a filter on day 1 of each 28-day cycle (every 4 weeks). Infusion rate may be reduced if an infusion reaction occurs.

In the absence of progression of disease or unacceptable toxicity, treatment with INCMGA00012 will continue based on physician criteria for up to 2 years.

Tumor assessments per RECIST v.1.1 and irRECIST will be performed approximately every 8 weeks (\pm 7 days) for the first 6 months and every 12 weeks (\pm 7 days) thereafter until PD, treatment discontinuation, the start of new anti-cancer treatment, withdrawal of consent, death, or the end of study (EoS), whichever occurs first. Tumor assessments will be performed on the specified schedule regardless of treatment delays.

The primary endpoint is ORR.

For estimation of ORR, CBR, DoR, PFS, and OS, tumor response will be based on RECIST v.1.1. In patients who continue treatment beyond radiographic PD per RECIST v.1.1, tumor response (ORR, CBR, and PFS) may continue to be assessed using irRECIST criteria until study treatment discontinuation.

Safety assessments will include the incidence, nature, and severity of AEs and laboratory abnormalities graded per the NCI-CTCAE v.5.0. Laboratory safety assessments will include the regular monitoring of hematology, blood chemistry, coagulation, and thyroid function testing.

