- The duration of response (DoR) is defined as the time from start dose of first tumor response (either CR or PR) to disease progression or death due to any cause. The DoR will be calculated for the patients with unconfirmed CR or PR.
- The Time to Progression (TTP) is defined as the time from start dose to objective tumor progression or clinical disease progression (TTP does not include deaths). Patients with no progression will be censored at the date of their last evaluable imaging previous 35 days after last dose administration date.
- The Time to Response (TTR) is defined as the time from start dose to unconfirmed ORR date. Patients without ORR will be censored at the date of their last evaluable imaging previous 35 days after last dose administration date.
- Maximum Tumor Shrinkage (best percentage of change from baseline in the size of target tumor lesions) is defined as the biggest percentage of tumor shrinkage from baseline (obtained from the sum of the largest diameters of the target lesions).

5.4.1.2 irRECIST

The following results will be reported in all patients and in patients with measurable disease:

- The response assessment of the tumor is defined as best response according to:
 - irCR: complete disappearance of all measurable and non-measurable lesions. Lymph nodes must decrease to < 10 mm in short axis. Confirmation of response is not mandatory.
 - irPR: decrease of $\geq 30\%$ in Total Measured Tumor Burden (TMTB) relative to baseline, non-target lesions are irNN, and no unequivocal progression of new non-measurable lesions.
 - irSD: failure to meet criteria for irCR or irPR in the absence of irPD.
 - irNN: no target disease was identified at baseline and at follow-up the patient fails to meet criteria for irCR or irPD.
 - irPD: minimum 20% increase and minimum 5 mm absolute increase in TMTB compared to nadir, or irPD for non-target or new non-measurable lesions. Confirmation of progression is recommended minimum 4 weeks after the first irPD assessment.
 - irNE, used in exceptional cases where insufficient data exists.

- irORR is defined as the proportion of participants with irCR or irPR. Participants who do not have on-study radiographic tumor re-evaluation, who received anti-tumor treatment other than the study medication prior to reaching an irCR or irPR, or who died, progressed, or dropped out for any reason prior to reaching an irCR or irPR will be counted as non-responders in the assessment of irORR.

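### SAP 5.4.1.2 has no irPD route for a small new measurable lesion that Protocol 6.4.4 can treat as confirmed irRECIST progression

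*SAP*

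**What the plan says.** SAP 5.4.1.2 gives three ways to reach irPD: "irPD: minimum 20% increase and minimum 5 mm absolute increase in TMTB compared to nadir, or irPD for non-target or new non-measurable lesions". The quantity behind the first is named in the irPR definition as "Total Measured Tumor Burden (TMTB) relative to baseline", but the SAP does not say which lesions go into it. The irPR definition excludes unequivocal progression of new non-measurable lesions and does not mention new measurable ones.

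Protocol 6.4.4 tells the investigator, when judging whether burden has changed, to "consider all target and non-target lesions as well as any incremental new lesion(s". It then lists five scenarios, any one of which confirms progression at repeat imaging. One is a size rule that begins "Tumor burden remains" and uses the same 20% and 5 mm limits against nadir. Two others have no size limit and apply to measurable and non-measurable lesions alike: "Additional new lesion(s) since last evaluation" and "New lesion resulting in initial PD is worse (qualitative assessment". The consequence is stated directly: "If repeat imaging confirms PD due to any of the scenarios listed above, subjects will be discontinued from study therapy". A later note allows an exception after consultation with the sponsor.

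On follow-up, SAP 1.4 says that irRECIST response "may continue to be assessed using irRECIST criteria until study treatment discontinuation", and Protocol 6.4.1 ends tumour assessments at progression or treatment discontinuation. Protocol 6.4.4 asks for continued imaging only in men who stop treatment without documented progression.

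**The concern.** The investigator and the analysis program would apply different definitions of irRECIST progression to the same scan. Take a man with an additional small measurable lesion, or a new measurable lesion that is worse on qualitative reading, while total burden stays under the SAP limits. He has confirmed progression for treatment purposes and comes off drug. In the SAP he is irSD, or irPR if burden is down enough.

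Later data may not correct this, because his imaging may end with treatment. The irPFS text in SAP 5.4.1.2 also has no explicit censoring rule for a living, assessed man without irPD.

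At stake are irPFS, 6-month irPFS, irCBR and possibly irORR. So is the RECIST versus irRECIST comparison planned in Protocol 8.4.3 and SAP 5.4.7: under the RECIST table in SAP 5.4.1.1 any new lesion is PD, so part of any difference would come from the missing route. SAP 5.7 lists two changes from the protocol, and this is not among them.

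**Working it through.** **The plan's own figures.** Neither document gives a figure for irPFS or irPD. The one design calculation, for ORR, reproduces: at least 3 responders of 16 gives exact one-sided alpha 0.0429 at 5% and power 0.803 at 25%, and 10% drop-out takes 16 to 18. It does not depend on irPD.

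**Step 1: compare the routes.**

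| Finding | Protocol 6.4.4 (confirmed at repeat scan) | SAP 5.4.1.2 irPD |
|---|---|---|
| Burden up at least 20% and 5 mm from nadir | Yes | Yes |
| Non-target progression | Yes | Yes |
| New non-measurable lesion progresses | Yes | Yes |
| Additional new measurable lesion, burden below limits | Yes | No |
| New measurable lesion worse on qualitative reading, burden below limits | Yes | No |

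**Step 2: which new measurable lesions fall in the gap?** Assume that TMTB includes new measurable lesions and that other lesions are stable. Lesion sizes are assumptions. A new lesion of L mm on a nadir sum of S mm reaches the 20% limit when L/S ≥ 0.20, that is S ≤ 5L. Every L below exceeds 5 mm.

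- L = 10 mm: SAP irPD up to S = 50 mm. At S = 60, 10/60 = 16.7%; at S = 100, 10/100 = 10%. Neither is irPD.
- L = 15 mm: up to S = 75 mm.
- L = 20 mm: up to S = 100 mm.
- L = 30 mm: up to S = 150 mm.

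On this reading the gap is small new measurable lesions in men with larger burden. If TMTB were meant to exclude new lesions, the gap would cover every new measurable lesion.

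**Step 3: can such a man count in irORR?** An assumed case: baseline sum 100 mm, first scan 80 mm. At the second scan old lesions total 55 mm and a 10 mm new lesion appears, so TMTB = 65 mm, down 35% from baseline: the irPR size criterion is met. At the repeat scan another 10 mm lesion appears, so TMTB = 75 mm, and 10/65 = 15.4% above nadir: no irPD. The protocol's additional-lesion scenario confirms progression. He can be an irORR responder. He can also enter irCBR more easily than RECIST CBR, since irCBR sets no minimum duration for irSD while SAP 5.4.1.1 requires 12 weeks.

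**Step 4: size per man.** With 18 men, if an affected man is counted as progression-free, a simple 6-month proportion moves by 1/18 = 5.6 points. For example, 4/18 = 22.2% (95% Clopper-Pearson CI 6.4 to 47.6) becomes 5/18 = 27.8% (9.7 to 53.5).

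For Kaplan-Meier, assume 8, 4 and 2 events at the first three 8-weekly scans and 4 men event-free. If k of the first 8 events become censorings at that scan, 6-month irPFS = (10 + k)/18 × 6/10 × 4/6:

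- k = 0: 22.2%
- k = 1: 24.4%
- k = 2: 26.7%
- k = 3: 28.9%

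The documents do not give k.

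**The case against.** **A reader might infer that the SAP leaves out progression by new measurable lesions altogether.** The text does not support that. A separate arm for new non-measurable lesions makes sense if measurable ones are already in the burden sum, and Protocol 6.4.4 brings incremental new lesions into the burden judgement. Only the sub-threshold subset is missed. What stands is that TMTB is undefined and the threshold-free routes are absent.

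**A reader might also infer that irPFS is biased upward overall.** That is not shown. The protocol scenarios say when a repeat scan confirms an initial progression. SAP irPFS takes the first documented irPD and only recommends confirmation, which pulls irPFS down relative to confirmed progression. Death also remains an event, unless the rule on two or more incomplete assessments removes it. These features soften or offset the effect but do not close the gap for the men concerned.

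**The silence of SAP 5.7 is weak evidence of an oversight.** SAP 1.1 is based on Protocol version 1.1 of 08-Nov-2019. The protocol supplied cites a September 2020 data cut-off and so is later, and the wording of 6.4.4 in version 1.1 cannot be seen. The current texts still disagree.

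**The endpoints carry limited weight.** SAP 3.4 makes the irRECIST endpoints exploratory, although SAP Table 2 also numbers irPFS, irORR and irCBR as Secondary 12 and 13, and SAP 5.4.3 treats all non-primary p-values as descriptive. This limits the consequence; the disagreement remains.

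**Conclusion.** The point holds for a defined subset: men whose irRECIST progression is confirmed by an additional or worsening new measurable lesion while TMTB stays below the 20% or 5 mm limit, with no other irPD criterion met. The protocol counts them as progressed and takes them off drug, barring an agreed exception. The SAP gives them no event unless they die or are later imaged with qualifying irPD. For these men irPFS and 6-month irPFS are lengthened and irCBR, possibly irORR, may count them favourably.

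The number affected cannot be derived from the documents and could be zero. Each such man is worth up to 5.6 points on a simple 6-month proportion and about 2.2 points in the Kaplan-Meier illustration, whose event pattern is assumed. Both are small beside the width of the intervals at n = 18. Net bias across the trial is not established. The primary ORR, RECIST PFS and the decision rule are untouched.

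**What to change.** In SAP 5.4.1.2:

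1. Keep the existing irPD criteria, including first irPD without mandatory repeat imaging. Replacing them with the five protocol scenarios would do harm: those need a repeat scan, and Protocol 6.4.4 does not require one for clinically unstable men, who could then lose their event.
2. State that TMTB includes new measurable lesions.
3. Add that progression confirmed under the new-lesion scenarios of Protocol 6.4.4 also counts as irPD in irPFS, 6-month irPFS, irORR and irCBR, and say which scan supplies the date.
4. In the same edit, state the irPFS censoring rule for a living, assessed man without irPD.

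The two texts should be reconciled without altering the protocol's treatment rule. If the difference is intended, declare and justify it in SAP 5.7.

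The cost is SAP wording and derivation programming before database lock. This assumes that the reason for irRECIST progression is captured, which the documents do not show and which should be checked against the eCRF. irPFS may look slightly less favourable.

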5.4.2 Primary Efficacy Analysis

ORR will be estimated with the 95% Clopper-Pearson confidence intervals and the P-value with exact binomial test.

Primary efficacy results will be reported for the FAS and PP set. Full analysis set will be considered the primary set for the analysis.

Table 1. Primary Efficacy Estimands

Estimand	Population	Variable	Intercurrent event strategy	Summary measure
Primary	FAS set	Unconfirmed ORR	- Patient with missing Unconfirmed ORR outcome will be considered as non-responders. - Patients without any post-baseline assessment will be considered as non-responders.	The number and proportion of patients with response with the 95% Pearson-Clopper CI will be calculated.
Sensitivity 1 to Primary	PP set	Unconfirmed ORR	Same as above	Same as above

5.4.3 Decision Rules and Adjustment of Alpha for Primary Endpoint

The study would be defined as positive at final analysis, if the ORR in the INCMGA00012 arm is statistically significantly better ($p<0.05$) than expected under the null hypothesis ($H_0: ORR \leq 5\%$). Decisions will be based on exact binomial test.

For all secondary and exploratory tests, we will use two-sided P-values with alpha=0.05 level of significance. The P-values emerging from these analyses will not be interpreted in a confirmative sense; they will be considered of descriptive nature only.

5.4.4 Secondary Efficacy Analysis

Secondary efficacy results will be reported for the FAS and PP set.

For binary endpoints, the number and proportion of patients with response with the 95% Pearson-Clopper CI will be calculated.

The time to event endpoints will be performed with maximum likelihood method (MLM) for exponential distribution test, at nominal level of 0.05. Number and percentage of events will be described. The median, 6-month, 1 and 2-year

survival rates and 95% confidence intervals will be provided based on exponential MLM and Kaplan-Meier method. Swimmer plots for time-to-event endpoints will be provided.

For continuous outcome (maximum tumor shrinkage) we will use statistics of central tendency (median with 95%CI) and dispersion (range and interquartile range). We will provide waterfall plots of maximum tumor shrinkage from baseline. The duration of response has also plotted with bar plots.

For all tests, we will use two-sided P-values with alpha=0.05 level of significance. P-values emerging from these analyses will not be interpreted in a confirmative sense; they will be considered of descriptive nature only.

Table 2. Secondary Efficacy Estimands

Estimand	Population	Variable	Intercurrent event strategy	Summary measure
Secondary 1	FAS set	PFS	
 - Patients with no progression or death will be censored at the date of their last evaluable imaging previous 35 days after last dose administration date. - If no post-baseline tumor assessment is available, patients will be censored at the date of treatment initiation + 1 day. - Data for patients with an event who missed two or more scheduled assessments immediately prior to the event will be censored at the last tumor assessment prior to the missed visits. 	
Kaplan-Meier plot, number and proportion of events, median survival time, 6 months, 1- and 2-year survival rates with corresponding 95% CI.
 
Swimmer plot will be provided.

Sensitivity 1 to Secondary 1	PP set	PFS	Same as above	Same as above
Secondary 2	FAS set	BOR	
 - When CR or PR is the best response across all time points, then best overall response will be unconfirmed CR or unconfirmed PR respectively. - When CR or PR is the best response for ≥ 4 weeks then best overall response will be confirmed CR or confirmed PR respectively. - When SD is the best response for ≥ 24 weeks the best overall response will be SD ≥ 24 w. - When SD is the best response for < 24 weeks the best overall response will be SD < 24 w. - When non-target disease only and Non-CR/Non-PD is the best response for ≥ 24 weeks the best overall response will be SD ≥ 24 w. - When non-target disease only and Non-CR/Non-PD is the best response for < 24 weeks the best overall response will be SD < 24 w. - When PD is the best response across all time points, best overall response will be PD. - When there is no evaluable tumor assessments best overall response will be NE. 	The number and proportion of patients with response with the 95% Pearson-Clopper CI will be calculated.
Sensitivity to secondary 2	PP set	BOR	Same as above	Same as above
Secondary 3	FAS set	Confirmed ORR	
 - Patient with missing confirmed ORR outcomes will be considered as no responders. - Patients without any post-baseline assessment will be considered as non-responders. 	The number and proportion of patients with response with the 95% Pearson-Clopper CI will be calculated.

Estimand	Population	Variable	Intercurrent event strategy	Summary measure
Sensitivity to secondary 3	PP set	Confirmed ORR	Same as above	Same as above
Secondary 4	FAS set	Unconfirmed CBR	
 - Patient with missing Unconfirmed ORR outcome will be considered as no responders. - Patients without any post-baseline assessment will be considered as non-responders. 	The number and proportion of patients with response with the 95% Pearson-Clopper CI will be calculated.
Sensitivity to secondary 4	PP set	Unconfirmed CBR	Same as above	Same as above
Secondary 5	FAS set	Confirmed CBR	
 - Patient with missing confirmed ORR outcomes will be considered as no responders. - Patients without any post-baseline assessment will be considered as non-responders. 	The number and proportion of patients with response with the 95% Pearson-Clopper CI will be calculated.
Sensitivity to secondary 5	PP set	Confirmed CBR	Same as above	Same as above
Secondary 7	FAS set	OS	
 - Patients who are not reported as having died will be analyzed as censored observations on the date they were last known to be alive. - If no post-baseline tumor assessment is available, patients will be censored at the date of treatment initiation + 1 day. 	Kaplan-Meier plot, number and proportion of events, median survival time, 1- and 2-year survival rates with corresponding 95% CI.
Sensitivity to secondary 7	PP set	OS	Same as above	Same as above
Secondary 8	FAS set	TTR	
 - Patients with no response will be censored at the date of their last evaluable imaging previous 35 days after last dose administration date. 	Kaplan-Meier plot, number and proportion of events, median survival time, 1- and 2-year survival rates with corresponding 95% CI.
Sensitivity to secondary 8	PP set	TTR	Same as above	Same as above
Secondary 9	FAS patients with overall response	DoR	
 - Patients with no progression or death will be censored at the date of their last evaluable imaging previous 35 days after last dose administration date. - If no post-response tumor assessment is available, patients will be censored at the date of treatment response + 1 day. - Data for patients with an event who missed two or more scheduled assessments immediately prior to the event will be censored at the last tumor assessment prior to the missed visits. 	Kaplan-Meier plot, number and proportion of events, median survival time, 1- and 2-year survival rates with corresponding 95% CI.
Sensitivity to secondary 9	PP patients with overall response	DoR	Same as above	Same as above
Secondary 11	FAS set	Maximum Tumor Shrinkage	Only observed cases will be used	Median, range, mean, standard deviation, and interquartile range. Waterfall plots describing the percentage of change in target tumor lesions
Sensitivity to secondary 11	PP set	Maximum Tumor Shrinkage	Same as above	Same as above

Estimand	Population	Variable	Intercurrent event strategy	Summary measure
Secondary 12	FAS set	irPFS	
 - Confirmation of progression is recommended minimum 4 weeks after the first irPD assessment - If no post-baseline tumor assessment is available, patients will be censored at the date of treatment initiation + 1 day. - Data for patients with an event who missed two or more scheduled assessments immediately prior to the event will be censored at the last tumor assessment prior to the missed visits. 	Kaplan-Meier plot, number and proportion of events, median survival time, 6-month, 1- and 2-year survival rates with corresponding 95% CI.
Sensitivity to secondary 12	PP set	irPFS	Same as above	Same as above
Secondary 13	FAS set	irORR	
 - Patient with missing confirmed ORR outcomes will be considered as no responders. - Patients without any post-baseline assessment will be considered as non-responders. 	The number and proportion of patients with response with the 95% Pearson-Clopper CI will be calculated.
Sensitivity to secondary 13	PP set	irORR	Same as above	Same as above
Secondary 13	FAS set	irCBR	
 - Patient with missing confirmed ORR outcomes will be considered as no responders. - Patients without any post-baseline assessment will be considered as non-responders. 	The number and proportion of patients with response with the 95% Pearson-Clopper CI will be calculated.
Sensitivity to secondary 13	PP set	irCBR	Same as above	Same as above

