8.4.7 Secondary Efficacy Outcomes

We will describe number and proportion of patients with clinical benefit and 6-month PFS. We will estimate the proportion with the 95% Pearson-Clopper confidence intervals. For time to event endpoints (PFS, OS, irPFS and DOR), we will use the Kaplan-Meier method. Number and proportion of events, median survival time and survival rates, with corresponding 95%CI, will be calculated in both arms. For continuous outcome (maximum tumor shrinkage) we will use statistics of central tendency (median with 95%CI) and dispersion [range and interquartile range]. We provide waterfall plots of maximum tumor shrinkage from baseline. The duration of response has also plotted with bar plots.

Analysis will be performed on the ITT, and PP sets. ITT will be considered the primary population for the analysis. For all tests, we will use two-sided p-values with $\alpha \leq 0.05$ level of significance.

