Confidence intervals will be presented to one more decimal place than the raw data. A two-sided significance level of 5% will be used for confidence intervals.

For binary endpoints, the 95% confidence intervals (CIs) will be constructed based on an exact binary distribution.

The Kaplan-Meier method will be used to estimate the time to event function, the median of time to event and the 95% confidence interval of the same will be calculated. These confidence intervals will be calculated based on the Greenwood method. Number and proportion of events, median survival time and survival rates, with corresponding 95%CI will be calculated.

All scores and change from baseline will be summarized in terms of the number of observations, mean, standard deviation, 95%CI of mean, median, range and interquartile range. We will examine the residuals to assess model assumptions.

All report outputs will be produced using SAS® version 9.4 version in a secure and validated environment. All report outputs will be provided to the Sponsor in a single Microsoft Word document.

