5.7 Changes of Analysis from Protocol

- The level of significance α has been changed from \leq to $=$ in some paragraphs.
- We have included the time to response as secondary endpoint. We have dropped the time to progression.

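### SAP 5.4.4 prescribes an exponential test with no null value and exponential estimates with no fit check, where the rest of the plan names only Kaplan-Meier

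*SAP*

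**What the plan says.** SAP 5.4.4 (Secondary Efficacy Analysis) sets the method for time-to-event endpoints in two sentences. The first is a test: "The time to event endpoints will be performed with maximum likelihood method (MLM) for exponential distribution test, at nominal level of 0.05". The second doubles the estimates: the median and the 6-month, 1- and 2-year "survival rates and 95% confidence intervals will be provided based on exponential MLM and Kaplan-Meier method". On testing, the section adds "For all tests, we will use two-sided P-values with alpha=0.05 level of significance" and "P-values emerging from these analyses will not be interpreted in a confirmative sense; they will be considered of descriptive nature only".

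Elsewhere only Kaplan-Meier appears:
- Protocol 8.4.7: "For time to event endpoints (PFS, OS, irPFS and DOR), we will use the Kaplan-Meier method".
- SAP 5.1: "The Kaplan-Meier method will be used to estimate the time to event function", with Greenwood intervals.
- SAP 5.4.5 bases the handling of withdrawals in the timed endpoints on Kaplan-Meier.
- SAP Table 2 lists a Kaplan-Meier plot with events, median and rates for PFS, OS, TTR, DoR and irPFS. It lists no exponential output and no test.

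The only hypothesis value in either document belongs to the response rate (null of 5% or less). SAP 5.4.3 ties the trial's success to it: "The study would be defined as positive at final analysis, if the ORR in the INCMGA00012 arm is statistically significantly better".

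SAP 5.7 lists two changes from the protocol. One concerns the sign attached to alpha. The other adds time to response, followed by "We have dropped the time to progression". The exponential model is not mentioned.

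**The concern.** A one-sample exponential test compares an estimated hazard with a reference hazard. With no reference, the programmer must choose one, possibly after seeing the data. Calling the p-value descriptive does not say what it tests.

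The exponential estimates raise a separate problem. They assume a hazard that stays constant over time, and the SAP plans no check of this. It also does not say which figure leads if the two methods disagree. Each endpoint could then carry two medians and two sets of rates.

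Constant hazard is hardest to defend for time to response, because most patients are expected never to respond. For PFS, irPFS and DoR, progression is found mainly at scans every 8 and later 12 weeks, and Protocol 1.8 expects long survival in many of those who respond.

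**Working it through.** **The plan's own figures.** No figure is given for any time-to-event test, so there is nothing to reproduce. The only calculated design is for response: at least 3 responders of 16, null 5%, target 25%. The exact binomial gives a one-sided error of 0.043 and power of 0.803, as the plan claims. That null cannot be carried over to a hazard.

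**Method.** The exponential estimate is rate λ = events / total observed time, median = ln 2 / λ, and proportion event-free at t = exp(−λt). Months are 30.4 days.

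**Time to response.** From the documents: 18 patients; scans at weeks 8, 16 and 24; non-responders censored at last evaluable imaging (SAP 5.4.1.1). Assumed: 3 of 18 (17%) or 25% respond, 70% of them at week 8 and 30% at week 16, a mean of 0.7 × 8 + 0.3 × 16 = 10.4 weeks. Non-responders are assumed to be observed for 18 to 29 weeks on average.
- 17%, 29 weeks: 3 × 10.4 + 15 × 29 = 466.2 weeks = 107.3 months. λ = 3 / 107.3 = 0.0280. Implied responding by 24 months: 1 − exp(−24 × 0.0280) = 49%.
- 25%, 18 weeks: 4.5 × 10.4 + 13.5 × 18 = 289.8 weeks = 66.7 months. λ = 4.5 / 66.7 = 0.0674. Implied: 1 − exp(−24 × 0.0674) = 80%.
- If non-responders leave sooner (half at week 8, a quarter each at weeks 16 and 24, mean 14 weeks), the same formula gives 73% and 86%.

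The actual proportions are 17% and 25% throughout. In simulated trials under the 14-week assumption, the Kaplan-Meier median was not reached in 91-98%, while the exponential model reported a median of about 8-13 months.

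**PFS, strong heterogeneity.** Assumed: 25% of patients with median 24 months, 75% with median 2 months; follow-up uniform over 12-24 months (12 months' recruitment, study end 12 months after the last patient starts); exact progression dates.
- True 6-month rate: 0.25 × 0.5^(6/24) + 0.75 × 0.5^(6/2) = 0.210 + 0.094 = 30%.
- True 2-year rate: 0.25 × 0.5 + 0.75 × 0.5^12 = 12.5%.
- True median: 2.9 months.
- Exponential, large sample: within each group, P(event) = 1 − [exp(−12h) − exp(−24h)] / (12h), with h = ln 2 / median, and mean time = P(event) / h. Events per patient: 0.25 × 0.402 + 0.75 × 0.996 = 0.848. Time per patient: 0.25 × 13.93 + 0.75 × 2.87 = 5.64 months. λ = 0.150, median 4.6 months.
- In 20,000 simulated trials of 18 patients, the typical (median) exponential results were: median 4.5 months, 6-month rate 40%, 2-year rate 2.5%.

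**Coverage of the exponential 95% interval (log-scale Wald), same setup, 25% / 75% split:**

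| Medians (months) | Median | 6 months | 2 years |
|---|---|---|---|
| 24 and 2 | 58% | 75% | 42% |
| 12 and 2 | 73% | 83% | 49% |
| 12 and 3 | 88% | 90% | 73% |
| 8 and 4 | 94% | 94% | 91% |
| 24 and 8 (OS-like) | 95% | 95% | 93% |

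**PFS, scan timing alone.** Here the hazard is truly constant but progression is seen only at scans. With a true median of 2 months, 6-month PFS is 22% exponential, 15% Kaplan-Meier and 12.5% true. With a true median of 4 months, the figures are 42%, 38% and 35%.

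**The case against.** A parametric estimate beside Kaplan-Meier is a legitimate choice in a trial of 18. With near-constant hazards it is unbiased and more precise. Even in the 24-and-2-month case the 6-month exponential interval is about 0.34 wide, against about 0.39 for Kaplan-Meier. The endpoints are secondary, the p-values are labelled descriptive, SAP 5.4 calls all efficacy analysis exploratory, and Kaplan-Meier is reported in any case. This stands, and it limits the importance of the point. It does not supply the missing null value or rescue time to response.

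A reader might infer more than the documents support:
- **That the model cannot fit any endpoint.** The protocol gives no hazard shape or PFS distribution, only a general remark about responders. Deaths need not wait for a scan, a near-constant hazard for OS is possible, and the table shows little harm under mild heterogeneity.
- **That the exponential intervals are simply too narrow.** The lost coverage comes mainly from bias under the assumed mixture. Where the model holds, a narrower interval is a real gain.
- **That the sponsor made an undeclared change.** The SAP is based on protocol version 1.1 of November 2019. The supplied protocol uses September 2020 data, so it is later. Version 1.1 is not available and might have contained the model.
- **That the 2-year rates are wholly extrapolated.** Recruitment is estimated at 12 months or more, and longer recruitment gives longer follow-up. The 2-year rate is also requested from Kaplan-Meier.

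Table 2 does suggest that Kaplan-Meier is the main method, but no sentence says so.

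**Conclusion.** The point holds in a limited form. The undefined test and the inconsistency within the SAP follow from the text alone. The omission from SAP 5.7 is shown only against the supplied protocol.

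Misfit differs by endpoint. For time to response it is structural, and the 49-80% implied responding rests on the assumed response rates, scan pattern and censoring times. For PFS, irPFS and DoR the assumption is doubtful. The PFS error ranges from serious (42-75% coverage at 24 against 2 months) to negligible (91-94% at 8 against 4 months), and the documents do not say which case is nearer. For OS misfit is not established.

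The response-rate analysis and the trial's success criterion are unaffected. The change should be made because it is easy and removes an analysis that cannot be carried out as specified.

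**What to change.** In SAP 5.4.4, delete the exponential test sentence and the reference to exponential estimates. Report Kaplan-Meier medians and rates with their intervals, as Protocol 8.4.7 states for PFS, OS, irPFS and DoR and as SAP Table 2 states for these and time to response.

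If the sponsor keeps exponential estimates for some endpoints, exclude time to response, name Kaplan-Meier as the reported estimate, add a fit check and list the addition in SAP 5.7. The test should still go: without a null value there is nothing to run.

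The cost is one sentence and one phrase, with less output to program. The loss is an estimate that could be slightly more precise if hazards are near constant.
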